11 APPENDICES

Appendix A – Summary of Protocol Amendments - Key Changes

Amendment	Change	Rationale
Protocol Version 2.0, Amendment 1 (revisions to Protocol Version 1.0)	Added pulse oximeter measurements as part of vital sign measurements to be carried out	At the request of the FDA
Protocol Version 3.0, Amendment 2 (revisions to Protocol Version 2.0)	Laboratory test change: requirement for INR and prothrombin time sampling and testing after Day 14 removed	As the last dose is taken on Day 5, analysis of INR and prothrombin time is only deemed necessary during the Acute Exacerbation Phase
Protocol Version 3.0, Amendment 2 (revisions to Protocol Version 2.0)	Reduction of ECG testing from triplicate to a single test	ECG are no longer required in triplicate by the Central Reader
Protocol Version 3.0, Amendment 2 (revisions to Protocol Version 2.0)	Addition of inflammation of cervix and vagina as an adverse event of special interest	Align with Investigator's Brochure at the request of the UK Regulatory Agency
Protocol Version 4.0, Amendment 3 (revisions to Protocol Version 3.0)	Modification of inclusion criterion 4 to reflect that spirometry in the past 12 months is required but the result does not need to be available before dosing.	Spirometry is being done at screening and this will be used to determine eligibility for the study. Historical data is required for data analysis demography only. If historical values are not available, pre and post bronchodilator spirometry will be conducted during the stabilization phase, for demographic purposes.
Protocol Version 4.0, Amendment 3 (revisions to Protocol Version 3.0)	Modification of inclusion criterion 5 to allow subjects who have given up smoking in the last 6 months into the study.	The impact of smoking cessation within 6 months is not significant to the patient assessment, within the trial.
Protocol Version 4.0, Amendment 3 (revisions to Protocol Version 3.0)	Increase of FEV1 to <65 % of the predicted normal value for inclusion criterion 6.	This will facilitate recruitment of the appropriate population and is not anticipated to adversely impact safety of subjects or efficacy outcomes.

Protocol Version 4.0, Amendment 3 (revisions to Protocol Version 3.0)	Removal of inclusion criterion 7 regarding post-bronchodilator spirometry.	In the acute exacerbation setting it is challenging to conduct pre and post bronchodilator spirometry. Therefore, all spirometry measurements will be performed 'on bronchodilator'.
Protocol Version 4.0, Amendment 3 (revisions to Protocol Version 3.0)	Update of regular medication requirements for inclusion criterion 9.	Restriction changed to allow the use of any short acting rescue medication to match with standard clinical practice.
Protocol Version 4.0, Amendment 3 (revisions to Protocol Version 3.0)	Removed exclusion criterion of history of allergic rhinitis and atopic disease.	Exclusion only for allergic asthma needed to ensure COPD is expected diagnosis. Rhinitis and atopic disease exclusion not required.
Protocol Version 4.0, Amendment 3 (revisions to Protocol Version 3.0)	Removal of macrolide and calcium channels blockers from exclusion criterion 3.	Removed to avoid replication as they are covered by exclusion criterion 9.
Protocol Version 4.0, Amendment 3 (revisions to Protocol Version 3.0)	Update of exclusion criterion 10 to reflect that only live vaccines should be withheld for 30 days before screening.	Non-live vaccines are required to be withheld for only 14 days, the period of the immune response to the vaccines.
Protocol Version 4.0, Amendment 3 (revisions to Protocol Version 3.0)	Removal of criterion 14 excluding those in whom anti-muscarinic agents are contraindicated.	Antimuscarinic use is not a requirement for study participation so this exclusion criterion is not required.
Protocol Version 4.0, Amendment 3 (revisions to Protocol Version 3.0)	Removal of exclusion criterion 20 for concomitant use of agents that prolong the QTc interval.	Recent PK/PD modelling of available clinical data indicates there is no concentration – QTc relationship with BCT197. The recent data, in addition to the available preclinical data, indicate that BCT197 at the concentrations predicted to be achieved would not prolong the QTc interval.
Protocol Version 4.0, Amendment 3 (revisions to Protocol Version 3.0)	Addition of excluded concomitant medication of P-gp inhibitors to exclusion criterion 19.	P-gp inhibitors were previously included in the list of excluded medications but not included as an exclusion criterion.

Protocol Version 4.0, Amendment 3 (revisions to Protocol Version 3.0)	Addition of exclusion criteria for subjects with pneumonia, pneumothorax or pulmonary embolus.	Subjects with these conditions should not be enrolled in the study, for subject safety.
Protocol Version 4.0, Amendment 3 (revisions to Protocol Version 3.0)	Modification of spirometry assessment and timings to reflect that all spirometry will be taken at least 1 hour after regular long acting bronchodilator administration and 30 minutes after a short acting bronchodilator rescue medication has been taken. For patients with acute exacerbation it is not practical to have FEV1 after bronchodilator wash out.	It is necessary to standardize baseline and post study drug assessment of spirometry as much as practically possible.
Protocol Version 4.0, Amendment 3 (revisions to Protocol Version 3.0)	Modification to timing of ECG assessments.	BCT197 would not be expected to be present in the body at 8, 12 and 26 weeks post dose and so ECGs at these time points have been removed. Additional ECGs have been added at dosing and PK sample times to increase safety monitoring and to allow for PK/PD analysis of QTc data around the time of maximum concentration BCT197 are included.
Protocol Version 4.0, Amendment 3 (revisions to Protocol Version 3.0)	Collection of baseline information on presence of specific symptoms of acute exacerbation (increased sputum production, increased cough and/or increased dyspnea).	Data required to better characterize the patient population.
Protocol Version 4.0, Amendment 3 (revisions to Protocol Version 3.0)	Addition of theophylline to permitted concomitant medications.	May form part of standard care.
Protocol Version 4.0, Amendment 3 (revisions to Protocol Version 3.0)	Six minute walk test has been reduced to single measurement at end of acute exacerbation.	The expectation is that subjects will be unable to perform this test due to their clinical condition in the early part of the exacerbation. A single measurement at

		day 14 gives adequate data.
Protocol Version 4.0, Amendment 3 (revisions to Protocol Version 3.0)	The composite score has been removed from Baseline Visit.	The composite score detects treatment failure so should not be included at Baseline.
Protocol Version 4.0, Amendment 3 (revisions to Protocol Version 3.0)	Inclusion of vaginal inflammation evaluation (history and if indicated by symptoms, examination).	Included following regulatory agency feedback.
Protocol Version 5.0, Amendment 4 (revisions to Protocol Version 4.0)	Azithromycin is no longer a prohibited medicine as an exclusion criteria	Results of a drug interaction study with BCT197 and azithromycin showed no clinically meaningful impact of concomitant dosing on BCT197 levels
Protocol Version 5.0, Amendment 4 (revisions to Protocol Version 4.0)	Clarification in prohibited meds that the P-gp inhibitor Azithromycin is not prohibited	Results of a drug interaction study with BCT197 and azithromycin showed no clinically meaningful impact of concomitant dosing on BCT197 levels
Protocol Version 5.0, Amendment 4 (revisions to Protocol Version 4.0)	Removal of exclusion of killed vaccine in last 14 days as exclusion criterion	No safety risk in administering killed vaccine.
Protocol Version 5.0, Amendment 4 (revisions to Protocol Version 4.0)	Removal of killed vaccine as a prohibited medication	No safety risk in administering killed vaccine.
Protocol Version 5.0, Amendment 4 (revisions to Protocol Version 4.0)	Removal of oral requirement for body temperature	There is no requirement for oral body temperature and any body site (oral, rectal, axillar, etc.) is suitable.
Protocol Version 5.0, Amendment 4 (revisions to Protocol Version 4.0)	Removal of exclusion criteria 7 - Subjects requiring long term (at least 12 hours daily) oxygen therapy for chronic hypoxemia	Reduction of respiratory testing procedures in the previous protocol amendment (v4) enables patients on long term oxygen therapy to undertake the required assessments during the study. Therefore, there is no longer any need to exclude patients on long term oxygen therapy.

Appendix B – Protocol Deviations Criteria List

The list of protocol deviations to be identified and to be included in the body of the CSR is defined as:

- Failure to obtain written informed consent prior to a patient's participation in the study (Randomised/ITT/PP/Safety/PK)
- Patient does not meet one or more of the inclusion criteria (PP)
- Patient meets one or more of the exclusion criteria (PP)
- Disallowed medications, as per Section 10.6 - Concomitant Therapy of the protocol (PP)
- Patient/Investigator unblinded to treatment
- Serious Breach of GCP
- Incorrect treatment allocation/taken wrong study medication (PP)
- Same medication number given to more than one patient
- Non-compliance with IMP administration [REDACTED] (ITT/PP/Safety/PK)
- Failure to complete spirometry assessments at visits 1-12; in particular failure to complete adequate measurement of the primary variable (i.e. Baseline and/or Day 7 FEV1 values not provided) (ITT/PP)
- Failure to complete BODE at Visit 9
- Failure to complete mMRC at visits 1, 7, 9, 10, 11 and 12
- Failure to obtain PK samples on 2 of the 3 dosing days (PK)
- Failure to complete CRQ at visits 1, 9, 10, 11 and 12
- Failure to report a SAE within timelines required by GCP, the protocol and applicable regulations
- Failure to report AEs of special interest as required by protocol
- Temperature excursion where IMP is stored (IMP dispensed to patient) (PP)
- Expired IMP administered to a patient (PP)
- Drug accountability incomplete to the extent that an IMP kit cannot be 100% traced from sponsor/warehouse to site and back (PP)
- Patient non-compliance with e-diary
- Lack of source data in the patient source – direct entry into the eCRF
- IRB/EC was not constituted in accordance with the establishment requirements
- IRB/EC review was conducted in an inappropriate procedure such as circulation etc. other than normal Meeting
- Study visit out-of-window as defined in the current protocol (PP)
- Missed study visit (PP)
- Missing Central Laboratory assessments
- Missing Respiratory Rate results
- Missing QTc Interval results.

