5 SAMPLE SIZE AND POWER

The sample size is based on a formal statistical calculation using the following assumptions:

1. Endpoint: Absolute change in FEV1 (mL) from baseline to Day 7
2. Minimum clinically significant difference between regimens: absolute change of 100 mL
3. Standard deviation (SD) of the difference = 230 mL (based on a previous study [CBCT197A2201] with BCT197)
4. Superiority design of two BCT197 doses compared to placebo
5. Two-sided alpha (Type 1) error = 0.05
6. No adjustment for multiplicity
7. Beta error (Type 2) = 0.20 (Power = 80%).

Based on the above assumptions, 85 subjects will need to be analysed per dose regimen, resulting in a total of 255 evaluable subjects.

Assuming a dropout rate of approximately 5%, a total of approximately 270 subjects will be randomised to the study.

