6.1 Intention-To-Treat population (ITT)

The ITT population includes all subjects who:

- Are randomised, and
- Receive at least one dose of study medication, and
- Provide a Baseline and at least one post-Baseline FEV1 value.

Patients will be included in the analysis per the treatment to which they were randomised.

Note: the 'Baseline' FEV1 value refers to the last non-missing FEV1 value assessed prior to the first dose of study medication.

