6.6 Protocol deviations/violations and exclusions from analysis sets

All violations and exclusions of patients from analysis populations will be finalised at the Classification Meeting prior to the final database lock (DBL)/study unblinding, through clinical review input provided by Mereo, using the following sources of information:

- Supportive patient listings, provided by the ICON lead statistician ahead of the Classification Meeting, based on data recorded on the eCRF.
The protocol deviations criteria are detailed in Appendix B and specific protocol deviations will be identified by programming.
- Protocol Deviation Logs, retrieved from Clinical Trial Management System (CTMS).

Further, deviations from protocol will be classified as major or minor.

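### SAP Appendix B tags a missing Day 7 FEV1 against the ITT set, which contradicts the ITT definition in SAP 6.1 and protocol 13.3.1

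*SAP*

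**What the plan says.** SAP 6.1 admits to ITT every randomised patient who took at least one dose and meets one FEV1 condition: "Provide a Baseline and at least one post-Baseline FEV1 value". Protocol 13.3.1 has the same three conditions. Neither mentions Day 7. SAP 6.3 places the Day 7 FEV1 requirement in the PP definition.

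SAP 6.6, on deviations and exclusions from analysis sets, says: "The protocol deviations criteria are detailed in Appendix B and specific protocol deviations will be identified by programming". It leaves the exclusions themselves to a Classification Meeting held before database lock and unblinding.

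Appendix B lists the deviations, many with population names in brackets. One bullet opens with failure to complete spirometry at visits 1 to 12, singles out the primary variable, and ends "Baseline and/or Day 7 FEV1 values not provided) (ITT/PP". A separate bullet for a missed study visit is tagged PP only. The meaning of the bracketed tags is not stated.

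**The concern.** Take a patient with a Baseline FEV1, values on Days 2 to 6 and none on Day 7. Under SAP 6.1 the patient is in ITT. Under the Appendix B tag, read in the light of 6.6, the patient is marked for removal from ITT. Two rules for the primary analysis set give different answers, and SAP Section 9 declares no change to the ITT definition.

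Such patients are the reason for using an MMRM. SAP 7.2.1 declines to impute because the model is valid when dropout is missing at random, and that argument needs patients with partial data to stay in. Day 7 can be missing for reasons tied to outcome. Protocol 10.6.1 keeps ventilated patients in the study even when assessments cannot be done. SAP 8.1.8 also removes spirometry of unacceptable quality before analysis.

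Secondary endpoints use ITT too. A patient with an early post-Baseline FEV1 who died before Day 7 would, under the tag, also leave the ITT comparison of COPD-related deaths.

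**Working it through.** **The passages side by side**, for a dosed patient with Baseline and Day 2 to 6 values but no Day 7 value:

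| Source | Status |
|---|---|
| SAP 6.1, protocol 13.3.1 | in ITT |
| SAP 6.3 | out of PP only |
| SAP 8.6.2.1 | contributes Days 2 to 6 to the MMRM |
| SAP 7.2.1 | kept, no imputation, missing at random assumed |
| SAP Appendix F | kept if any one post-randomisation value is valid and covariates are complete |
| Appendix B, missed visit | affects PP |
| Appendix B, spirometry bullet | affects ITT and PP |

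The last row stands alone. In the Appendix F worked example, patients 1 and 2 have no Visit 7 value and both are retained.

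**The plan's sample size** (SAP Section 5). Inputs: "Minimum clinically significant difference between regimens: absolute change of 100 mL"; "Standard deviation (SD) of the difference = 230 mL", used here as the SD of the change in each arm; two-sided alpha 0.05; power 80%.

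- n per arm = 2 × (1.960 + 0.842)² × 230² / 100² = 83.1, so 84 by normal approximation. The noncentral t calculation gives 85 (power 0.805), the stated figure.
- 255 / 0.95 = 268.4, so 269, which agrees with approximately 270, or 90 per arm.

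**Power if patients without Day 7 are removed.** The documents give no rate of missing Day 7 FEV1, so 5% to 20% is an assumed range. Power = Φ(100 / (230 × √(2/n)) − 1.960), with n = 90 × (1 − proportion missing).

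| Missing at Day 7 | n per arm | Total | Power |
|---|---|---|---|
| 5% | 85.5 | 256.5 | 0.81 |
| 10% | 81 | 243 | 0.79 |
| 15% | 76.5 | 229.5 | 0.77 |
| 20% | 72 | 216 | 0.74 |

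**Illustrative bias.** None of these assumptions comes from the documents, except that the SD and the true difference match SAP Section 5:

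- six visits, SD 230 mL, AR(1) correlation 0.8;
- mean change rising linearly from 20 to 100 mL on placebo and from 40 to 200 mL on active, so the true Day 7 difference is 100 mL;
- permanent dropout, more likely after a low value at the previous visit (logistic, slope 2 per SD);
- 300,000 simulated patients per arm.

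| Missing, placebo / active | Day 7 completers (mL) | Likelihood under missing at random (mL) |
|---|---|---|
| 5% / 5% | 99.9 | 99.7 |
| 10% / 10% | 100.3 | 100.4 |
| 10% / 5% | 90.9 | 100.4 |
| 15% / 5% | 81.6 | 99.9 |
| 20% / 10% | 81.3 | 99.4 |

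With equal missingness the completer estimate is essentially unbiased. With more loss on placebo it falls, because low placebo values are removed. More loss on active would push it the other way.

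**The case against.** The strongest reply is that Appendix B is a list of deviations to report, not a set of automatic exclusions. SAP 6.6 says that deviations are identified by programming, while exclusions are settled at a meeting with clinical input. Other tags also fail as automatic rules. Any failed inclusion criterion is tagged PP, although 6.3 asks only for key criteria. Missing PK samples on two dosing days is tagged PK, although 6.4 needs one quantifiable concentration. Read literally, the disputed bullet would even remove a patient from ITT for a missed Week 26 spirometry. The literal reading would also leave the Day 7 criterion in 6.3 with nothing to do, since every ITT patient would already meet it. All this suggests that 6.1 was the intention.

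That limits the consequence but does not remove the conflict. The section on exclusions points to this list, SAP 8.3 tabulates exclusions from each population with reasons, and nothing says that Section 6 prevails over the tags.

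A reader might infer three stronger things that the documents do not support.

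- *That the primary MMRM has become a Day 7 completer analysis.* This would follow only if the meeting applied the tag over 6.1, 7.2.1 and Appendix F.
- *That the item "Non-compliance with IMP administration", tagged for ITT, PP, Safety and PK, contradicts 6.1 and 6.2.* Part of its text is blacked out. It may mean that no study drug was taken, which would agree with both definitions.
- *That 13 to 14 patients would be lost* (270 × 0.05 = 13.5). The 5% is the general dropout allowance; the 255 patients it leaves are those expected to complete the study and follow-up. It is not a rate of missing Day 7 FEV1.

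**Conclusion.** Wrong as written. The ITT tag on a missing Day 7 FEV1 conflicts with the ITT definition in both documents, with 6.3, with the missing-data rationale and worked example, and with Appendix B's own tag for a missed visit.

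The consequence is conditional. If the tag were applied, every patient in the primary set would have a Day 7 value. Earlier visits would then add little to the Day 7 contrast, which would come close to the observed-case ANCOVA of SAP 8.6.2.3. The sample size is unaffected, and power stays at 0.81 if 5% miss Day 7. The risk is bias, and it needs missingness that is both related to outcome and different between arms. The simulated shortfalls of about 9 to 19 mL on a true 100 mL rest wholly on the assumptions listed and are not a forecast for this trial.

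**What to change.** Before unblinding, amend SAP Appendix B and Section 6.6:

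- Split the bullet in two: no Baseline FEV1 or no post-Baseline FEV1 (ITT/PP); no Day 7 FEV1 (PP).
- Leave other missed spirometry without an ITT tag.
- Say what the bracketed tags mean.
- State that the population definitions in Section 6 prevail where a tag disagrees.

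For the partly redacted dosing item, the sponsor need only confirm that its full wording agrees with the one-dose definitions in 6.1 and 6.2.

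The cost is one reworded bullet and two added sentences. Data collection, the model and the sample size do not change.

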Appendix C – EXACT Scoring Instructions

1. Computing EXACT Daily Scores

Raw Scores

Raw scores are assigned to each item response option, as shown in [Table 1](#) of this Appendix. Note that items 3, 8, 9, 10, 11, and 14 have unique scoring instructions. Item responses should be converted to item-level scores as the first step in scoring.

The recommended programming for the electronic EXACT diary does not allow a study patient to skip individual items. If a patient tries to skip a question, a message should appear to prompt the patient to complete the question. Thus, no missing data are expected for individual items in the electronic data capture setting. If missing values do occur for individual items, the scores for that day cannot be calculated and should be set to missing.

EXACT Total Score

An EXACT Total score should be computed for each day of diary collection. The EXACT Total score is based on a logit scoring system with conversion to a 0 to 100 scale for ease of interpretation and use. The scores are computed using a simple conversion table, by hand or electronically (e.g., software data interface for ePRO devices or statistical software, such as SAS®). To compute the EXACT Total score:

Convert each original item response code to an item-level raw score, by matching the responses to [Table 1](#) below. For example, for question 1, if the data-collection form or system encodes the response of “Not at all” as code 1, recode it to a zero (0) to match [Table 1](#), question 1. Note that some questions group certain original item response codes into a single item-level raw score; for example, question 3 groups original responses of “A little” and “Some” into the item-level raw score of 1.

Sum the item-level raw scores of the 14 EXACT items to form the raw summed score.

Note: do not sum the original item responses; sum the recoded values obtained in the step described above.

For each raw summed score, look up the corresponding EXACT Total score from [Table 2](#) of this appendix. The EXACT Total score ranges from 0 to 100. Sample SAS program code for converting raw summed scores to the EXACT Total score is provided in [Table 4](#) of this appendix.

If the EXACT Total score is 0, change it to missing. This scoring rule is based on previous validation work demonstrating that moderate-to-severe COPD patients will experience symptom(s) each day, and a score of zero on all 14 EXACT items is likely to represent a situation where in order to complete the diary quickly, the respondent did not accurately report their daily symptom(s).

Where no diary entry exists for a given day, create a record in the data file for that day and enter a missing value for the EXACT Total score. Each day a patient is followed in the study must have a record for the day, even if there is no data and the EXACT Total score is missing.

Domain Scores

Three respiratory symptom domains are also embedded within the EXACT measure: Breathlessness, Cough & Sputum, and Chest Symptoms.

To compute domain scores:

Item assignments to domains are as follows. Please note that items 4, 12, 13, and 14 do not correspond to a domain score and are not used in domain-specific analyses.

- Breathlessness – Items 7, 8, 9, 10, and 11
- Cough & Sputum – Items 2 and 3
- Chest Symptoms – Items 1, 5, and 6.

For each day, sum the item-level raw scores of the items comprising the domain to form the domain raw summed score. If no diary entry exists for a given day, leave the domain raw summed score missing.

Each domain raw summed score has its corresponding “EXACT Domain” score. For each domain raw summed score, look up the corresponding EXACT domain score from [Table 3](#) below. If no diary entry exists for a given day, leave the EXACT domain score missing.

If the daily EXACT domain score is 0, change it to missing. This scoring rule is based on previous validation work demonstrating that moderate to severe COPD patients will experience symptom(s) each day, and a score of zero on all 14 EXACT items is likely to represent a situation where in order to complete the diary quickly, the respondent did not accurately report their daily symptom(s).

2. Computing Event Frequency, Duration, and Severity

All exacerbation parameters are based on the EXACT Total score.

Baseline EXACT Total Score

For studies enrolling patients during a stable baseline period, baseline EXACT values are computed and used to identify the onset of EXACT events.

For MBCT206 study, as there is no stable period during which EXACT-PRO scores are collected prior to administering the study drug, the definition of the Baseline EXACT-PRO from the user manual will not be used for Acute Exacerbation Phase.

The score and subscores obtained on Day 1 of the EXACT-PRO observation period, which corresponds to Study Day 1, will be used as the baseline for Acute Exacerbation Phase.

Nevertheless, the definition of the Baseline EXACT-PRO from the user manual will be used for Stabilisation Phase. Baseline is defined as a period during which the patient is considered within

his/her condition as stable or their usual state. The Baseline EXACT-PRO score (or subscores) for Stabilisation Phase will therefore be defined as the mean of EXACT-PRO scores from the first 7 days of the Stabilisation Phase (Week 3; Days 15-21), with a minimum of 4 days of available data required to compute the baseline value. If 4 or more of the first 7 days of data are not available, the baseline EXACT-PRO score for Stabilisation Phase will not be calculated.

Resetting Baseline EXACT Total Score (Stabilisation Phase)

Over the course of the trial, Baseline should be reset every 4 weeks (28 days) in the absence of an EXACT-based event to allow for improvements or deterioration in disease state over time, as follows:

Event-free Periods (Stable Reset Baseline – Baseline_{SR#})

For patients who do not experience an EXACT-based event during Weeks 4 to 7 of the study, Baseline is reset beginning Day 1, Week 8. Data from the last 7 days of the 4 week period (Week 7; Days 43–49) are used for this purpose, with a minimum of 4 days of data required to compute the reset value (Baseline_{SR1}; mean within patient-score over 7 days). If fewer than 4 days of data are available, the Baseline will not be reset; the previous Baseline value (i.e. mean of EXACT-PRO scores from the first 7 days of the Stabilisation Phase (Week 3; Days 15-21)) will be used until the next reset period.

Using this reset Baseline (Baseline_{SR1}), the data are examined moving forward from Week 8, Day 1 for evidence of an EXACT-based event during the subsequent 4 weeks (Week 8, Day 1 to Week 11, Day 7). In the absence of such an event, the Baseline is reset again (Baseline_{SR2}) beginning Day 1, Week 12. Data from the last 7 days of the 4 week period (Week 11; Days 1–7) are used for this purpose, with a minimum of 4 days of data required to compute the reset value (Baseline_{SR2}). If fewer than 4 days of data are available, the Baseline will not be reset; the previous Baseline value will be used until the next reset period.

The resetting process continues every 28 days throughout the duration of the study or until an EXACT event occurs (see instructions below).

Re-Setting Following an EXACT Event (Event Reset Baseline – Baseline_{ER#})

If or when an EXACT event occurs during the Stabilisation Phase, the patient's Baseline value is re-established following recovery. To reset Baseline values following an exacerbation, the patient's mean EXACT score during the fourth week following Recovery (Days 22–28 post-Recovery) is used. If the patient experiences a new EXACT event during this 4 week period (Days 1 to 28 post-Recovery), the Baseline is not reset until the fourth week following Recovery from that subsequent event. A minimum of 4 days of data are required to reset Baseline. If fewer than 4 days of data are available, the Baseline will not be reset; the previous Baseline value (i.e. mean of EXACT-PRO scores from the first 7 days of the Stabilisation Phase (Week 3; Days 15-21)) will be used until the next reset period.

The reset Baseline following Recovery from the first exacerbation (Baseline_{ER1}) is used to identify subsequent events during the next 4 week period. In the absence of an event during this 4 week period, the Baseline value is reset again (Baseline_{ER2}), beginning Recovery Week 9, Day 1, using data from the final 7 days of the 4-week event-free period (Recovery Week 8; Days 1–7 post-Recovery). If fewer than 4 days of data are available, the Baseline will not be reset; the previous Baseline value will be used until the next reset period.

This process of resetting Baseline in the absence of an EXACT event continues through the duration of the study.

Event Frequency (Stabilisation Phase)

Two parameters are required to identify event frequency: (1) Baseline and (2) Onset. Baseline has been previously described for Acute Exacerbation Phase and for Stabilisation Phase. Due to the design of the study, the EXACT-PRO user manual definition of “Onset” will not be used for Acute Exacerbation Phase, and the EXACT-PRO value on Study Day 1 will replace the “Onset” in the definitions. Therefore, event frequency will not be identified for Acute exacerbation Phase.

Nevertheless, the EXACT-PRO user manual definition of “Onset” will be used for Stabilisation Phase. Onset is defined as the first day in which the patient experiences an acute, sustained worsening of their baseline condition. Therefore, event frequency will be identified for Stabilisation Phase.

Onset

Onset is identified in 1 of 2 ways: *Either* (1) an increase in EXACT score ≥ 12 points above the patient’s mean Baseline for 2 consecutive days, with Day 1 of the 2 days serving as Day₁ (Onset) of the event **OR** (2) an increase ≥ 9 points above the patient’s mean Baseline for 3 consecutive days, with Day 1 of the 3 days serving as Day₁ (Onset) of the event. The presence of either constitutes Onset of an event during the Stabilisation Phase. Note that the requirement of consecutive days is the reason the data file must have a record for every day for a patient, even if the EXACT score is missing.

Event Duration (Stabilisation Phase)

Event Duration requires identification of the following parameters: (1) Onset; (2) 3-day Rolling Average; (3) Maximum Observed Value; (4) Threshold for Improvement; and (5) Recovery. It is possible that Improvement may occur at multiple timepoints during an event and that this Improvement may or may not reflect full Recovery. As the EXACT-PRO user manual definition of “Onset” will not be used for Acute Exacerbation Phase, event duration will not be identified for Acute Exacerbation Phase. Nevertheless, the 4 other parameters will be identified for Acute Exacerbation Phase as below.

On the other hand, the EXACT-PRO user manual definition of “Onset” will be used and event duration will be identified for Stabilisation Phase. Therefore, the 5 parameters will be identified for

Stabilisation Phase as below.

Three-day Rolling Average

A 3-day Rolling Average is used to account for day-to-day variability in EXACT scores. This is operationalized as a 3-day Rolling of the mean EXACT score [Day_{x-1}, Day_x, Day_{x+1}] initiated on Study Day 1 (Onset) and ends on Day 1 of recovery.

The 3-day Rolling Average will be calculated from Study Day 1 to Day 1 of recovery:

- At Day 1, the Rolling Average will be the total score of Study Day 1 (Onset), and will be missing if the total score of Study Day 1 is missing
- At Day 2 the Rolling Average will be the total score of Study Day 2, and will be missing if the total score of Study Day 2 is missing
- The Rolling Average at any other Day x (including Day 1 of recovery) will be computed as the mean of Study Day_{x-1}, Day_x, Day_{x+1}, if at least one of Day_{x-1}, Day_x, Day_{x+1} is available.

Only 1 of the 3 data points needs to be present for this computation.

Improvement from Day 1 in EXACT-PRO Rolling Average will be calculated as:

Improvement from Day 1 = Rolling Average at Day 1 - Rolling Average at Day x

The improvement from Day 1 in EXACT-PRO Rolling Average will be left missing if the Rolling Average at Day 1 cannot be computed or if it is missing at Day x.

Maximum Observed Value between Day 1 and Day 14

The Maximum Observed Value (MOV) is the highest Rolling Average EXACT score observed in the context of an EXACT exacerbation within the first 14 days of the exacerbation (i.e. between Day 1 and Day 14). The MOV is allowed to increase over the first 14 days of an exacerbation. Starting on Day 15 of an exacerbation, the MOV stays at the level on the 14th day for the remainder of the exacerbation.

Threshold for Improvement

Improvement is defined as a decrease in the Rolling Average EXACT score ≥ 9 points from the previous day's MOV during an event.

Recovery

Recovery is defined as the first day in which a patient experiences a persistent, sustained improvement in their condition over the observed period. Improvement must be present for 7 consecutive days. The first day of the 7-day period is designated as the first day of Recovery (Day_R).

Based on the scoring algorithm for Recovery, EXACT exacerbations can be categorized as Recovered, Censored, or Persistent Worsening. Recovered is defined as an EXACT exacerbation meeting the Recovery definition outline above. Censored is defined as an EXACT exacerbation that began within 28 days of study termination and did not meet the Recovery definition during that

time period. Persistent Worsening is defined as an EXACT exacerbation that never meets the Recovery criteria, i.e., the patient's EXACT scores never meet the Recovery definition. All analyses including Recovery should be based on resolved events only, unless otherwise specified.

New Event (Stabilisation Phase)

Score increases consistent with Onset and occurring any time after the 7th day of the Recovery period are counted as a new event. To identify a new exacerbation, use the last available Baseline value. The reset Baseline value ($\text{Baseline}_{\text{RX}}$) is used if a patient's Baseline was re-established prior to the EXACT exacerbation; otherwise the original Baseline value from Stabilisation Phase (i.e. mean EXACT score during the first 7 days of the Stabilisation Phase (Week 3; Days 15-21)) is used. If no new event is experienced during the 4 week period post-Recovery, Baseline is reset in the manner described previously. There may be a new event beginning on the day after the day of recovery, but not on the day of recovery.

Duration (Stabilisation Phase)

Duration is the length of time in days from Onset to Recovery. Duration is calculated as the difference, in days, between the day of Onset (Day_1) and the day of Recovery (Day_R). The day of Recovery (Day_R) is not included in calculating Duration days.

Event Severity (Stabilisation Phase)

Severity is the highest EXACT Total score of the observation period from Onset (Day_1) to Recovery (Day_R), not using the 3-day Rolling Average. For patients who do not recover severity is the highest EXACT Total score of the observation period.

Table 1: Annotated EXACT for Raw Score Assignment

The following annotates the raw item-level score values associated with each text response for the EXACT items.

1. Did your chest feel congested today?	0. Not at all
	1. Slightly
	2. Moderately
	3. Severely
	4. Extremely
2. How often did you cough today?	0. Not at all
	1. Rarely
	2. Occasionally
	3. Frequently
	4. Almost constantly
3. How much mucus (phlegm) did you bring up when coughing today?	0. None at all
	1. A little
	1. Some
	2. A great deal
	3. A very great deal
NOTE: Score "A little" and "Some" the same.	
4. How difficult was it to bring up mucus (phlegm) today?	0. Not at all
	1. Slightly
	2. Moderately
	3. Quite a bit
	4. Extremely
5. Did you have chest discomfort today?	0. Not at all
	1. Slight
	2. Moderate
	3. Severe
	4. Extreme
6. Did your chest feel tight today?	0. Not at all
	1. Slightly
	2. Moderately
	3. Severely
	4. Extremely

7. Were you breathless today?	0. Not at all 1. Slightly 2. Moderately 3. Severely 4. Extremely
8. Describe how breathless you were today:	0. Unaware of breathlessness 1. Breathless during strenuous activity 2. Breathless during light activity 3. Breathless when washing or dressing 3. Present when resting NOTE: Score "Breathless when washing or dressing" and "Present when resting" the same.
9. Were you short of breath today when performing your usual personal care activities like washing or dressing?	0. Not at all 1. Slightly 2. Moderately 3. Severely 3. Extremely 4. Too breathless to do these NOTE: Score "Severely" and "Extremely" the same.
10. Were you short of breath today when performing your usual indoor activities like cleaning or household work?	0. Not at all 1. Slightly 2. Moderately 3. Severely 3. Extremely 3. Too breathless to do these NOTE: Score "Severely," "Extremely," and "Too breathless to do these" the same.
11. Were you short of breath today when performing your usual activities outside the home such as yard work or errands?	0. Not at all 1. Slightly 2. Moderately 3. Severely 3. Extremely 3. Too breathless to do these NOTE: Score "Severely," "Extremely," and "Too breathless to do these" the same.

12. Were you tired or weak today?	0. Not at all 1. Slightly 2. Moderately 3. Severely 4. Extremely
13. Last night, was your sleep disturbed?	0. Not at all 1. Slightly 2. Moderately 3. Severely 4. Extremely
14. How scared or worried were you about your lung problems today?	0. Not at all 1. Slightly 2. Moderately 3. Severely 3. Extremely NOTE: Score "Severely" and "Extremely" the same.

Table 2: Raw Summed Score to Scale Score Conversion Table for EXACT Total Score

Raw Summed Score	EXACT® Total Score	Raw Summed Score (continued)	EXACT® Total Score
0	0	26	50
1	8	27	51
2	13	28	52
3	17	29	53
4	20	30	54
5	23	31	55
6	25	32	57
7	27	33	58
8	28	34	59
9	30	35	60
10	31	36	61
11	33	37	63
12	34	38	64
13	36	39	65
14	37	40	67
15	38	41	68
16	39	42	70
17	40	43	72
18	41	44	73
19	42	45	75
20	43	46	77
21	44	47	80
22	46	48	83
23	47	49	87
24	48	50	92
25	49	51	100

This conversion table converts raw summed scores to a 0 to 100 scale, for ease of interpretation.

Table 3: Raw Summed Score to Scale Score Conversion Table for EXACT Domains

Domain Raw Summed Score ^a	Breathlessness Domain Score	Cough & Sputum Domain Score	Chest Symptoms Domain Score
0	0	0	0
1	11	13	12
2	19	25	23
3	25	39	31
4	30	56	38
